7. SAFETY ANALYSIS

Safety endpoints include AEs, clinical laboratory variables, vital signs, ECG variables including ECG interpretation, and physical examination.

Unless otherwise specified, all safety analysis will be performed by disease group (IgAN and C3G), according to the treatment the subject actually received using the Safety Population. For subjects from the other disease group, all safety data will be only listed in the listings.

All data will be presented for Part B and Part A + B. Change from baseline is defined as change from Part B baseline and change from Part A + B baseline.

For categorical data, proportions will be based on the number of subjects who have the opportunity to be assessed at that visit.

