#### 16.2.3.1. Adverse Events

TEAEs are defined as those AEs that develop or worsen after the first dose of study medication and up to 8 weeks beyond the last dose of study medication. The current version of MedDRA at the time of analysis will be used to classify all AEs.

TEAEs will be summarized by System Organ Class and Preferred Term, in accordance with the MedDRA coding dictionary. The number of subjects reporting each AE Preferred Term will be tabulated for all TEAEs and separately for those considered as possibly related to study treatment by the investigator. Number of subjects reporting SAEs will also be tabulated. AE summaries will be presented for each period of the study separately within each complement-mediated glomerulopathy group.

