1. INTRODUCTION

This statistical analysis plan (SAP) describes detailed statistical methods to be used for analysis and data presentation for reporting safety and biologic activity data of investigational infusion of APL-2 for Apellis study protocol APL2-201 for Part B only.

The planned length of participation in the study Part A (Core Study Phase) for each subject is 76 weeks, including an approximate 4-week screening period, 48-week treatment period and 24-week follow-up period. Following Day 336 and the completion of Part A, any subject who, in the opinion of the investigator, is experiencing clinical benefit from APL-2 administration will be invited to participate in Part B, a Long-Term Extension Phase in order to continue to receive treatment with APL-2 until it is commercially available for the disease under treatment. If invited to participate in Part B, the subject can enter the Long-Term Extension Phase as soon as they complete the 48-week treatment period and do not need to participate in the 24-week follow-up period.

Statistical Analysis Plan Version 1.0 was used to produce the Part A (Core Study Phase) analysis. This SAP will present the results for the final analysis for subjects who rolled over into Part B, presenting the safety and efficacy results of Part B (Long-Term Extension Phase) and Part A + B as Part B subjects in Part B data and as well as Part A data. Definitions for the study days and baselines are outlined in Section 13. This document has been prepared according to study protocol amendment 7.0 dated 07 July 2022.

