4.2. Safety Population/Intent-to-Treat (ITT) Population

Safety Set will only include the subjects who roll over to Part B and receive at least one dose of 1080 mg APL-2.

The definition of Intent-to-Treat (ITT) Population is the same as Safety Population. It will be used for efficacy endpoint analysis.

4.3. **Per Protocol Population**

The Per Protocol (PP) Population will only include subjects who were in the PP set in Part A and roll over to Part B and have not violated any inclusion or exclusion criteria and/or deviated from the protocol in a way that could influence their efficacy assessment while on study in Part B.

The PP Set will be used in efficacy analyses for Part B and Part A + B.

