5. STUDY SUBJECTS

Unless otherwise specified, study subjects will be summarized by disease group for Part B and Part A + B. The disease groups are defined throughout as patients with IgAN, LN, or C3G. For subjects from the other disease group, all efficacy data will be listed in the listings.

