7.1. Adverse Events

Adverse events (AEs) will be coded using the most recent version of MedDRA.

Severity of AEs will be assessed and classified into mild, moderate, severe, life-threatening or death by investigators. Handling rules for missing severity of AEs are described in Section 13.6.4.

Treatment emergent adverse events (TEAEs) are defined as those AEs that develop or worsen after the first dose of study medication and up to 56 days beyond the last dose of study drug.

AEs are classified as related if AEs are definitely related, probably related or possibly related to study drug; Any AEs with missing or unknown relationship will be considered as related to study drug.

All summaries of AEs described in this section will be on TEAEs. All summaries will be ordered by decreasing frequency of number of subjects in PT within SOC. In the case of equal frequency of number of subjects in SOCs or PTs, then summaries of AEs will be sorted alphabetically.

All summary tables will be presented for Part B and Part A + B, where AEs will be categorized by the Part in which the AE started, i.e. an AE which began during the Part A will be categorized under Part A even if it continues into Part B.

An overall summary for AEs including number of subjects who experience a TEAE, number of total TEAEs and number of unique TEAEs will be provided:

- TEAE
- APL-2-related TEAE
 - Related
 - Not related
- Infusion-related TEAEs
 - Related
 - Not related

- Serious TEAE
- Maximum severity of TEAEs
- Infusion site reaction (yes/no)
- TEAE leading to APL-2 withdrawn
- TEAE leading to dose interruption
- TEAE leading to death

The following summary will be provided by disease group for Part B and Part A + B:

- TEAEs by SOC and PT
- APL-2 Related TEAEs by SOC and PT
- Infusion-Related TEAEs by SOC and PT
- Serious TEAEs by SOC and PT
- TEAE by SOC, PT and maximum severity
- TEAE leading to APL-2 discontinuation by SOC and PT
- TEAE leading to dose interruption by SOC and PT
- TEAE leading to death by SOC and PT

If a SOC or PT was reported more than once for a subject, the subject would only be counted once in the incidence for that SOC or PT.

For subjects experiencing the same PT at multiple severities, the occurrence of the AEs with the greatest severity will be used in the analysis of incidence by severity.

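### The Part B and Part A + B safety tables cover IgAN and C3G only, so a rolled-over lupus nephritis subject is in the Safety Set but in no incidence rate

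*SAP*

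**What the plan says.** SAP 2.0 covers Part B, and Part A + B for the subjects who rolled over. Part A was handled elsewhere: "Statistical Analysis Plan Version 1.0 was used to produce the Part A (Core Study Phase) analysis" (SAP 1).

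- **Who is in the safety analysis.** SAP 4.2: "Safety Set will only include the subjects who roll over to Part B and receive at least one dose of 1080 mg APL-2". No disease is excluded.
- **Which groups are summarised for safety.** SAP 7 sets the default, unless something else is specified: "all safety analysis will be performed by disease group (IgAN and C3G" are the two groups named there. It continues: "For subjects from the other disease group, all safety data will be only listed in the listings".
- **AE tables.** SAP 7.1 begins with "An overall summary for AEs including number of subjects who experience a TEAE". The tables by system organ class and preferred term, including serious events and events leading to death, follow under: "The following summary will be provided by disease group for Part B and Part A + B".
- **Which groups Section 5 uses.** SAP 5: "The disease groups are defined throughout as patients with IgAN, LN, or C3G". This governs exposure (5.5), compliance (5.6) and protocol deviations (5.7).
- **What the protocol asks.** Protocol 16.2 plans summaries of every endpoint by diagnosis and names all four diseases. Protocol 16.2.3 evaluates safety in the safety population, which 16.2.1.2 defines as everyone dosed. Protocol 16.2.3.1: "AE summaries will be presented for each period of the study separately within each complement-mediated glomerulopathy group". The Synopsis (Statistical Methods) also allows pooling across diseases, as an option.
- **Declared changes.** SAP 15.1, on changes to the protocol's analyses, is marked not applicable.

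**The concern.** Safety is one of the two primary objectives (Protocol 9.1, SAP 2.1). As the SAP is written, a serious or fatal event in a rolled-over LN subject would be in a listing but would not add to any numerator in the Part B or Part A + B safety tables, and the subject would not be in any denominator. Because Section 5 includes LN and Section 7 does not, the exposure tables and the AE tables of one report would describe different sets of subjects, and a reader who set one against the other would not be told so. SAP 12 plans no safety monitoring committee for Part B, so the summary tables carry more of the weight.

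**Working it through.** The point is textual. The check is whether any later text overrides the Section 7 default, and what follows if none does.

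**Step 1. Look for an exception in SAP 7.1 to 7.4.**
- 7.1: the organ-class and preferred-term tables are explicitly by disease group. The overview table that precedes them does not state its columns, so the Section 7 default applies to it.
- 7.2: laboratory summaries, shift tables and liver abnormalities are by disease group.
- 7.3: vital signs are by disease group.
- 7.4: ECG interpretation is by disease group. The summary of ECG intervals names only the analysis visit, so the default applies again.
- No total, overall or pooled column is specified in any of the four.

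**Step 2. Set the outputs side by side.**

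| Source | Subjects | Disease groups summarised | Pooling across diseases stated? |
|---|---|---|---|
| SAP 5.5 to 5.7 (exposure, compliance, deviations) | Safety Population | IgAN, LN, C3G | No |
| SAP 7.1 to 7.4 (safety) | Safety Population | IgAN, C3G | No |
| SAP 8.1 and 9.1 (PK, PD) | PK and PD Populations | Disease groups, with a two-subject minimum when also split by dose | Yes, by dose group over all patients |
| Protocol 16.2, 16.2.3, 16.2.3.1 | Everyone dosed | All four diseases | Optional (Synopsis) |

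Rows 1 and 2 use the same population but different lists of groups. Row 3 shows that the SAP does pool over diseases where it wants a figure from all patients. Row 4 shows the departure from the protocol.

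**Step 3. Does the protocol rule reach Part B?** SAP 15.2 notes that the protocol defines no separate objectives or endpoints for Part B. However, Protocol Appendix 1 (A1.1) states that whatever it does not describe is the same as in the main protocol, and it describes no safety analysis. The Part A + B tables in any case contain Part A data. The rule therefore applies, and SAP 15.1 is where a departure should be declared.

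**Step 4. Effect on a reported rate.** Let n be the IgAN and C3G subjects in the Safety Set and x those with a given event. Let k be the listing-only subjects and y those with the event.

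- Section 7 tables taken together: x / n.
- Whole Safety Population: (x + y) / (n + k).
- Difference: (x + y)/(n + k) − x/n = [k/(n + k)] × (y/k − x/n).

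If the only case is in an LN subject (x = 0, y = 1), the tables show 0/n and the whole population gives 1/(n + k). The two agree for every event only if k = 0.

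**Step 5. Size.** The documents give none of n, k, x or y for Part B. No numerical magnitude follows.

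**The case against.** The strongest points on the other side are these.

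- **Nothing is lost.** SAP 7.1 provides listings for the Safety Population of all AEs, serious AEs, deaths, discontinuations and related events, with no disease restriction. This stands. The gap is in rates and denominators, not in disclosure.
- **A total column may be intended.** SAP 5.3 and 5.4 sort by frequency over all subjects, which suggests that totals exist in those tables, and the 7.1 overview is not labelled by disease group. This is possible, but Section 7.1 has no such sorting wording for AEs, no table shells are supplied, and the Section 7 default is explicit. Even a pooled overview would not bring LN events into the tables by organ class and preferred term.
- **The groups may be very small.** LN biomarkers are listing-only (SAP 5.2.3, 6.3), which fits a small LN group. That is a fair reason against a separate LN column. It is no reason to leave these subjects out of a total.
- **Pooling is optional in the protocol.** True, but summaries within each disease group are not optional, and the SAP provides neither for LN.

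A reader might also infer that an overall column improves detection. The protocol's own formula, 1 − (1 − p)^n, gives 71.8% for a 10% event with 12 subjects (the protocol states 72%), 92.0% with 24 and 99.4% with 48. These are chances that an event occurs among n subjects. Table layout does not change them, since the same subjects are observed and listed either way, so they do not measure this problem.

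**Conclusion.** The point holds for the outputs of SAP 2.0. Section 7 leaves any rolled-over LN subject out of every safety summary while SAP 4.2 keeps that subject in the Safety Set. SAP 5 and 7 contradict each other on LN, and the departure from Protocol 16.2.3 and 16.2.3.1 is undeclared. No size can be given, because Part B group sizes are not in the documents.

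Three stronger readings are not supported:

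- **That these subjects' events are in no incidence rate anywhere in the study.** Part A was reported under SAP 1.0, which is not among the documents, so its tables cannot be judged.
- **That treated primary MN subjects are left out.** Nothing shows that any entered Part B. SAP 2.1 and the SAP 5 group list omit MN, SAP 6.3 has no PLA2R analysis, and Section 7 speaks of one other group. This fits no MN subject in Part B but does not prove it, so the MN part is conditional.
- **That up to half of the subjects are affected.** That comes from the planned 1:1:1:1 enrolment into the study. Entry to Part B depends on perceived benefit and the investigator's invitation, so the planned ratio says nothing about the Part B mix.

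The conclusion assumes that the Section 7 default governs wherever 7.1 to 7.4 are silent, and that at least one LN subject received 1080 mg in Part B. If none did, and no MN subject did either, only the inconsistency in the text remains.

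**What to change.** 1. Add an 'All subjects' column, with the whole Safety Population as its base, to every summary table under SAP 7.1 to 7.4, for Part B and for Part A + B.
2. Use one list of disease groups in SAP 5 and SAP 7, and say which diseases the phrase about the other group refers to.
3. If LN (or MN) still has no column of its own, record this in SAP 15.1 as a departure from Protocol 16.2.3.1, with the reason.

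Separate LN or MN columns are optional where numbers are very small: a one-subject column can show only 0% or 100%. The total column alone closes the gap in rates and denominators.

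The cost is one extra column per table. No new data are needed, and the IgAN and C3G columns stay as they are. The pooled rate mixes diseases, so it should stand beside the disease columns and not replace them.

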7.1. Adverse Events

Adverse events (AEs) will be coded using the most recent version of MedDRA.

Severity of AEs will be assessed and classified into mild, moderate, severe, life-threatening or death by investigators. Handling rules for missing severity of AEs are described in Section 13.6.4.

Treatment emergent adverse events (TEAEs) are defined as those AEs that develop or worsen after the first dose of study medication and up to 56 days beyond the last dose of study drug.

AEs are classified as related if AEs are definitely related, probably related or possibly related to study drug; Any AEs with missing or unknown relationship will be considered as related to study drug.

All summaries of AEs described in this section will be on TEAEs. All summaries will be ordered by decreasing frequency of number of subjects in PT within SOC. In the case of equal frequency of number of subjects in SOCs or PTs, then summaries of AEs will be sorted alphabetically.

All summary tables will be presented for Part B and Part A + B, where AEs will be categorized by the Part in which the AE started, i.e. an AE which began during the Part A will be categorized under Part A even if it continues into Part B.

An overall summary for AEs including number of subjects who experience a TEAE, number of total TEAEs and number of unique TEAEs will be provided:

- TEAE
- APL-2-related TEAE
 - Related
 - Not related
- Infusion-related TEAEs
 - Related
 - Not related

- Serious TEAE
- Maximum severity of TEAEs
- Infusion site reaction (yes/no)
- TEAE leading to APL-2 withdrawn
- TEAE leading to dose interruption
- TEAE leading to death

The following summary will be provided by disease group for Part B and Part A + B:

- TEAEs by SOC and PT
- APL-2 Related TEAEs by SOC and PT
- Infusion-Related TEAEs by SOC and PT
- Serious TEAEs by SOC and PT
- TEAE by SOC, PT and maximum severity
- TEAE leading to APL-2 discontinuation by SOC and PT
- TEAE leading to dose interruption by SOC and PT
- TEAE leading to death by SOC and PT

If a SOC or PT was reported more than once for a subject, the subject would only be counted once in the incidence for that SOC or PT.

For subjects experiencing the same PT at multiple severities, the occurrence of the AEs with the greatest severity will be used in the analysis of incidence by severity.

For subjects experiencing the same PT at multiple relationship levels, the occurrence of the AEs with the strongest relationship to study drug will be used in the analysis of incidence by relationship to study drug.

The following listings will be provided for the Safety Population:

- All AEs
- Serious Adverse Events
- AEs leading to study drug discontinuation
- AEs leading to study discontinuation
- Death
- APL-2 Related TEAEs
- Infusion-Related TEAEs

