#### 15.1.2. Serious Adverse Events

An SAE is any AE or suspected adverse reaction that, in the view of the investigator, results in death, is life threatening, requires inpatient hospitalization or prolongation of existing hospitalization, results in a persistent or significant incapacity or substantial disruption of the ability to conduct normal life functions, or is a congenital anomaly or birth defect.

Important medical events that may not result in death, be life threatening\*, or require hospitalization may be considered serious when, according to appropriate medical judgment, they may jeopardize the subject or may require medical or surgical intervention to prevent one of the outcomes listed in the above definition.

Examples of important medical events include allergic bronchospasm requiring intensive treatment in an emergency room or at home, blood dyscrasias or convulsions that do not result in inpatient hospitalization, or the development of drug dependency or drug abuse.

\*Life threatening is defined as an AE or suspected adverse reaction that, in the view of either the investigator or sponsor, placed the subject at immediate risk of death as it occurred. It does not include an AE or suspected adverse reaction that, had it occurred in a more severe form, might have caused death.

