### 15.2.1. Relationship to Study Drug

The investigator will review each event and assess its relationship to study drug treatment (not related, unlikely related, possibly related, or definitely related). The date and time of onset, time relationship to drug dosing, duration, severity, action taken, and outcome (recovered/resolved, recovered/resolved with sequelae, recovering/resolving, not recovered/not resolved, fatal, or unknown) of each event will be noted.

Table 4 should be considered when evaluating the relationship of AEs/SAEs to study treatment.

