### 15.2.2. Severity of Events

The investigator will review each event and assess its severity. Note that severity is a measure of intensity, whereas seriousness is defined by the criteria in Section 15.1.2. An AE can be of severe intensity but not be considered serious.

Table 5 presents the severity definitions that should be considered when evaluating the severity of AEs and SAEs.

**Table 5:** Severity of Events

Severity	Definition
Mild	Event results in mild or transient discomfort, not requiring intervention or treatment; does not limit or interfere with daily activities (eg, insomnia, mild headache).
Moderate	Event is sufficiently discomforting so as to limit or interfere with daily activities; may require interventional treatment (eg, febrile illness requiring oral medication).
Severe	Event results in significant symptoms that prevents normal daily activities; may require hospitalization or invasive intervention (eg, anemia resulting in blood transfusion).

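### SAP 7.1 tabulates maximum severity on five grades where the protocol defines three; if data follow the protocol, the life-threatening and death grades will be empty whatever happens

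*SAP*

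**What the plan says.** SAP 7.1 (Adverse Events) states that the severity of AEs will be assessed and "classified into mild, moderate, severe, life-threatening or death by investigators". It places maximum severity in the overall AE summary and adds a table by system organ class, preferred term and maximum severity. The overall summary also has rows for serious TEAEs and for TEAEs leading to death. Each of these has its own table by class and term, and SAEs and deaths are listed.

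Protocol 15.2.2 says: "Table 5 presents the severity definitions that should be considered when evaluating the severity of AEs and SAEs". Table 5 has three rows: mild, moderate and severe. The top row reads "Event results in significant symptoms that prevents normal daily activities; may require hospitalization or invasive intervention". The same section draws a line between two concepts: "Note that severity is a measure of intensity, whereas seriousness is defined by the criteria in Section 15.1.2". Protocol 15.1.2 puts the extra SAP levels on the seriousness side of that line, where an SAE is an event that "results in death, is life threatening, requires inpatient hospitalization or prolongation of existing hospitalization", among other criteria. Protocol 15.2.1 also records fatal as an outcome.

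On causality, protocol 15.2.1 gives four levels ("not related, unlikely related, possibly related, or definitely related"), while SAP 7.1 says "AEs are classified as related if AEs are definitely related, probably related or possibly related to study drug".

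SAP 15.1, which is the place to record changes from the protocol's analyses, has the entry not applicable.

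**The concern.** The SAP attributes to investigators a classification that the protocol does not ask them to make. A table shell built from SAP 7.1 will carry life-threatening and death as severity grades. If the database holds only the three Table 5 grades, nothing can fill those rows, and a zero there says nothing about safety. A reader of the report could take it as a finding.

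This touches a named endpoint. Safety is part of the primary objective, and SAP 2.1.4 and protocol 9.2.6 both list the incidence and severity of AEs as a safety endpoint. The life-threatening row matters most, because it is the only place in the SAP's AE summaries where life-threatening events are named.

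**Working it through.** No figure in the plan underlies this point, so the check compares the scales level by level.

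| SAP 7.1 severity grade | In protocol Table 5? | Where the protocol records it |
|---|---|---|
| Mild | Yes | Severity |
| Moderate | Yes | Severity |
| Severe | Yes | Severity (top grade) |
| Life-threatening | No | Seriousness criterion (15.1.2), recorded for each AE (15.2) |
| Death | No | Seriousness criterion (15.1.2) and fatal outcome (15.2.1) |

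Grades without a protocol counterpart: 5 − 3 = 2.

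**Is this a version artefact?** SAP 1 says the SAP was prepared to protocol amendment 7.0, dated 07 July 2022. The protocol supplied is Amendment 7, and its current section 15.2.2 has three grades. The mismatch is between current texts.

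**What the tables would show if data follow Table 5.** Let d be the number of subjects with a fatal TEAE and t the number with a life-threatening TEAE.

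- The row for TEAEs leading to death shows d. The death grade under maximum severity shows 0. For any d ≥ 1, the two rows of the same overall summary disagree.
- The life-threatening grade shows 0 for any t. These subjects are counted under serious TEAEs, since life-threatening is an SAE criterion, but are not separated there from, for example, hospitalisations.
- Each such event carries one of the three Table 5 grades, so it is graded at most severe.

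**Can the information be recovered?** Yes. Protocol 15.2 has the investigator report both the intensity and the seriousness criteria met for each AE, and 15.2.1 records the outcome. Both counts can be derived from fields that the protocol already requires.

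**Causality.** SAP 7.1 reports only two classes, related and not related. Apart from missing or unknown relationship, which goes to related, the rule is

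related = definitely + probably + possibly.

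On the protocol's four levels, probably = 0, so related = definitely + possibly. No count changes. The remaining protocol level, unlikely related, is not named in the SAP rule. It falls to not related by default, which agrees with its definition in protocol Table 4, where a causal relationship is described as not reasonably possible.

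**The case against.** The strongest objection is that the eCRF is not in the documents. SAP version 2.0 follows a version already used for the Part A analysis, and it says plainly that investigators assign the five levels. It may describe the fields as built, or it may be template text; the documents do not settle which. A reader might infer that the two rows are empty by construction. The documents do not support that without the condition that data follow Table 5. The condition does not remove the need to act: if the eCRF has five grades, investigators are using two that the protocol never defines, and SAP 15.1 does not say so.

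Four other inferences go too far.

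- *Life-threatening and fatal events would appear as severe.* The protocol grades intensity separately from seriousness, so the investigator may choose any of the three grades. At most severe is all that can be said.
- *Deaths or serious events would be hidden.* They would not: both have a summary row, a table and a listing. What is missing is a separate count of life-threatening events.
- *The causality wording distorts the related counts.* It does not, as shown above.
- *Imputing missing on-treatment severity as severe (SAP 13.6.4) is too lenient on a five-grade scale.* Severe is the worst grade on the protocol scale. Going higher on the SAP scale would mean calling an event life-threatening or fatal only because its grade was blank. The rule is not a defect.

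It is also fair to say that the study is descriptive, with no formal inference, so no test or decision rule is shown to turn on these tables.

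**Conclusion.** The point holds as an undeclared contradiction between SAP 7.1 and protocol 15.2.2. Two of five severity grades have no basis in the protocol. Provided that data are collected per Table 5, those rows of the maximum-severity tables would be empty regardless of events, the death grade could conflict with the row for TEAEs leading to death, and life-threatening TEAEs would have no count of their own. No efficacy result, analysis population or related/not related count is affected. The consequence is limited to how a named safety endpoint is displayed and read, but it is worth correcting before the tables are produced.

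**What to change.** 1. In SAP 7.1, replace the five-level scale with the three grades of protocol Table 5 and tabulate maximum severity on those.
2. Add a row for life-threatening TEAEs to the overall summary, derived from the seriousness criterion recorded under protocol 15.2. Fatal TEAEs need nothing new, because they already have a row and a table.
3. Check the eCRF first. If it does collect five grades, reconcile protocol Table 5 with the SAP so that the two extra grades are defined, and declare the departure in SAP 15.1.
4. As a tidy-up with no effect on counts, delete probably related from the causality rule and state that unlikely related maps to not related.

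The cost is SAP wording, table shells and one derived row. If data were captured as the protocol requires, no new data are needed.

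### SAP 7.1 places adverse events by onset only and defines no Part B TEAE, so Part A events that worsen in Part B can be missing from the Part B tables

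*SAP*

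**What the plan says.** **Assignment to a part.** SAP 7.1 states that "AEs will be categorized by the Part in which the AE started", and explains that "an AE which began during the Part A will be categorized under Part A even if it continues into Part B". The explanation covers an event that carries on. Neither it nor any other sentence makes an exception for an event that gets worse.

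**Definition of a TEAE.** SAP 7.1 defines TEAEs as "those AEs that develop or worsen after the first dose of study medication", within a window after the last dose. Protocol 16.2.3.1 uses the same anchor: "TEAEs are defined as those AEs that develop or worsen after the first dose of study medication". Neither document gives a separate definition for Part B.

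**Tables.** SAP 7.1 says "All summary tables will be presented for Part B and Part A + B". They cover all TEAEs, drug-related and infusion-related TEAEs, serious TEAEs, maximum severity, discontinuation, dose interruption and death. Where a subject has the same preferred term at several severities, "the occurrence of the AEs with the greatest severity will be used in the analysis of incidence by severity". Under SAP 7 the tabulated groups are IgAN and C3G; other subjects are listed only. Protocol 16.2.3.1 also asks for a split by period: "AE summaries will be presented for each period of the study separately within each complement-mediated glomerulopathy group".

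**Recording a change in severity.** Protocol 15.2.2 says "The investigator will review each event and assess its severity". It does not say whether an increase in severity opens a new record with its own start date or updates the existing one.

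**The concern.** The Part B tables are the new safety output of this SAP, because Part A was reported under SAP Version 1.0. They should show what happened to subjects during the extension. A rule based on onset alone shows new events but not the deterioration of existing ones.

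This matters at Part B entry because subjects not already on twice-weekly dosing change regimen there (SAP 3.1). With the regimen they change formulation and infusion volume, from 9 mL mannitol to 20 mL sorbitol (Protocol 12.1). An infusion-site or other event that was mild before the change and intensified after it is one plausible form of a safety signal, and the Part B tables would not show it. SAP 12 plans no safety monitoring committee for Part B and SAP 6 rules out formal inference, so the descriptive tables carry most of the aggregate safety message.

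**Working it through.** **Step 1: apply the two rules to one case.** Take an event that starts after dosing in Part A, is mild, is ongoing at Part B entry, and becomes severe or serious in Part B.

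- *Is it a TEAE?* Yes. It developed after the first study dose.
- *To which part does it belong?* Part A, because it started there.
- *Is it in the Part B tables?* If it is kept as one record, no. This applies to every Part B AE table, including serious, maximum severity, discontinuation, interruption and death.
- *Is it in the Part A + B tables?* Yes, at its greatest severity. It is also in the listings in SAP 7.1.

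**Step 2: change one fact.** If the worsening is entered as a new record, its start date falls in Part B. It is then counted in the Part B tables and nothing is lost. The current text requires neither practice. The amendment summary says that procedures for severity changes in Section 15.2.2 were updated, but it does not give the rule.

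**Step 3: compare with the other safety data.** SAP 7 presents change from a separate Part B baseline, defined in SAP 13.3, and SAP 7.2 to 7.4 apply this to laboratory, vital-sign and ECG data. Deterioration after Part B entry is therefore visible for those data. AEs have no corresponding anchor.

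**Step 4: size.** The plan gives no figure for this point. Three inputs would be needed: the number of subjects in Part B (SAP 3.2 gives none), the number of Part A events still ongoing at entry, and the share that worsen. None is in the documents, so the undercount cannot be computed. What can be given is the effect of one omitted subject, if a Part B group had the 6 to 12 subjects planned per disease at enrolment (Protocol 16.1). That is an assumption for Part B:

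- n = 12: 1/12 = 8.3 percentage points
- n = 6: 1/6 = 16.7 percentage points

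Smaller groups would give larger steps.

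**Step 5: illustration by assumption.** Protocol 16.1 uses P(at least one case) = 1 − (1 − p)^n. Its figures reproduce: for n = 6, 46.9%, 73.8%, 88.2% and 95.3% at p = 10%, 20%, 30% and 40%; for n = 12, 71.8% and 93.1% at p = 10% and 20%. Now let p = 20% be the true Part B incidence of new or worsened events. Let m be the share of affected subjects whose only Part B harm is worsening of a Part A event kept as one record. The table then sees p(1 − m):

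| n | m = 0 | m = 25% (visible 15%) | m = 50% (visible 10%) |
|---|---|---|---|
| 6 | 73.8% | 62.3% | 46.9% |
| 12 | 93.1% | 85.8% | 71.8% |

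The values of p and m are chosen for illustration, not estimated. If worsening is always a new record, m = 0.

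**The case against.** **The rule conflicts with the SAP's own TEAE definition.** A reader might infer this, but the documents do not support it. The definition is anchored to the first study dose and decides whether an event is treatment-emergent. The onset sentence is a separate step that decides the part. The event in question satisfies both, and no sentence re-anchors worsening to Part B entry. What is missing is a Part B definition.

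**The event is counted only in Part A, with its Part A severity inflated.** A reader might infer this too. It does not hold: SAP 7.1 plans no Part A-only table, and the event appears in the Part A + B tables and the listings.

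**Nothing may be lost at all.** If sites enter a worsening as a new record, the Part B tables are complete. The SAP wording on one preferred term at several severities fits that practice but does not prove it. This stands, and it makes the undercount conditional. It does not remove the point, because the result should not depend on a convention the documents leave unstated.

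**Listings are enough in a small descriptive study, and Part B entry is not always the regimen boundary.** Both have weight. Subjects may switch from Week 24, and Protocol A1.1.3.2 expects at most a small fall in exposure on moving to twice-weekly dosing. The documents therefore do not show that worsening is the expected form of a signal. Still, the pooled tables cannot date a worsening relative to Part B entry, and the SAP does not say that the listings will show when severity changed.

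**Conclusion.** The point holds as a conditional weakness in the Part B safety tables. SAP 7.1 places events by onset alone and has no Part B TEAE. A Part A event that worsens or becomes serious in Part B is therefore absent from the Part B tables whenever it is kept as one record. Those tables can undercount harm; the documents do not establish that they will. The event is not lost from the reporting as a whole.

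The size is unknown. The 8 to 17 points per omitted subject rest on an assumed 6 to 12 subjects per Part B group, and the detection probabilities rest on assumed values of p and m. The change is worth making because it is cheap and gives AEs a Part B anchor like the one other safety data already have.

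**What to change.** Add to SAP 7.1 a definition: a Part B TEAE is an AE that starts, increases in severity or becomes serious on or after the first Part B dose, within the existing window after the last dose. State in the same place how worsening is recorded: as a new record, or as a dated change to the existing one. Count each event once in Part A + B.

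Alternatively, keep the onset rule and add one Part B table of Part A-onset AEs that worsened or became serious in Part B.

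The cost is a sentence or two in the SAP and minor programming. If the database holds only the greatest severity with no date of change, the definition cannot be programmed directly. The affected events would then have to be found by reviewing Part A-onset AEs that were ongoing at the first Part B dose. The downside is that an event that started in Part A can also appear in the Part B table, so a footnote should say so.
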